5.5.6 Collection of Human Biological Specimens

Human biological samples will be collected for this study; blood and tissue.

Bloodwork: A blood sample (15 mls) will be drawn for hematological analysis including a CBC with differential panel, coagulation studies to include prothrombin time (PT) and international normalized ratio (INR) and comprehensive metabolic panel (CMP) at screening pre-treatment and at Week 1 post-ReCell treatment, which is consistent with standard of care practices. Samples will be labeled and processed by WRNMMC laboratory medicine per institutional policy. Therefore, these samples will be labeled with subject identifiers. Additional laboratory testing will be performed only as clinically indicated. Any leftover blood from sample will be discarded per WRNMMC policy.

Punch biopsy: A tissue sample size of 3mm diameter will be obtained pre-treatment (baseline) from the INTEGRA™ MBWM treated wound site and adjacent normal skin and from the control and ReCell treated sites at at Week 2, 4 and 12 post-ReCell treatment. All tissue samples will be coded and labeled with the subject's 3-digit ID number, date and time of harvest. Tissue samples will be cut in half with a sterile scalpel; one half of the sample will be preserved in 10% formalin by a member

of the study team then delivered to Annapath Inc. via courier pick-up for tissue processing, embedding (paraffin blocks), microtomy and slide preparation as per Annapath, Inc Technical Guidelines and Annapath, Inc Procedure Protocol (see Appendix F and Appendix G). The other half of tissue sample will be flash frozen with liquid nitrogen then stored in a -80° freezer with alarm system located within the Department of Orthopaedics Biomedical Lab Room 2010, Building 19 (America).

As previously mentioned, one half of the tissue sample obtained for histology analysis will be frozen. The rationale for doing this is to preserve the ability to return to the frozen sample, if need be, in the event we do not get immunohistochemical analysis staining needed from the formalin fixed slides. Oftentimes formalin fixed tissue does not perform as expected therefore, necessitating the need to freeze part of the sample to preserve options. The frozen samples will only be stored for evaluation within the period of funding for this research project then destroyed as per institutional policy standards.

5.5.7 Banking of Human Biological Specimens

This clinical trial does not involve the long-term storage (banking) of biological specimens.

- **Where and how specimens will be stored** (including shipping procedures, storage plan, etc.): One half of the tissue specimen obtained from the surgical punch biopsies of the treated wound (performed at pre-treatment, Week 2, 4 and 12) and of normal adjacent skin will initially be sent to Annapath, Inc. for processing (slide preparation and paraffin block embedding) as per Annapath, Inc Technical Guidelines and Annapath, Inc Procedure Protocol (*see Appendix F and Appendix G*). Annapath, Inc. will coordinate and dispatch its own courier for tissue specimen pick-up at WRNMMC. Annapath, Inc. will return all slides and paraffin blocks to WRNMMC for analysis and storage. The prepared slides and paraffin blocks will be housed in a locked cabinet within the Department of Orthopaedics Biomedical Lab Room 2010, Building 19 (America). The other half of the tissue specimen will be flash frozen with liquid nitrogen obtained from the WRNMMC Biomedical Research Laboratory (BRL) then stored in a -80° freezer with alarm system located within the Department of Orthopaedics Biomedical Lab Room 2010, Building 19 (America).
- **How specimens will be labeled** (Specimens should be coded without any personal identifiers): No personal identifiers will be used in the coding of human specimens. All tissue samples will be coded and labeled with the subject's 3-digit ID number.

Who will have the access to the specimens, the clinical information, and the linkage: Annapath, Inc. laboratory staff will have access to coded tissue specimens up until the time they are processed and returned to WRNMMC. The study investigators will have access to the stored frozen samples, prepared slides and paraffin blocks. The information linking with the subject's 3-digit ID number to the name of the participant will be kept by the Principal Investigator or designee in the study regulatory files in a locked cabinet.

- **How specimens will be used (general and/or specific use):** The baseline histological analysis will examine the vasculogenesis and cytology of the regenerate before ReCell treatment. Serial samples will be analyzed to confirm

- the thickness of new tissue and assess the normality of structures present in the newly regenerated skin.
- **Specify the length of time that specimens will be stored:** The frozen samples and paraffin blocks will be housed in the Department of Orthopaedics Biomechanical Lab, Room 2010, Building 19 (America) and will be destroyed at the end of study completion. No specimens will be stored for future research. Slides will be stored according to institutional policy.
 - **How the confidentiality will be protected at the storage and at the time of distribution:** Please see section on confidentiality.
 - **Whether subjects will be contacted and consented for future uses:** At this time, we do not anticipate contacting subjects in the future for other uses of their stored tissue samples.
Approval process for future studies: At this time, we do not have plans for future studies. Should this change, the PI will seek sub-protocol IRB approval for any future related studies.
 - **How subjects may withdraw their specimens from storage:** Research participants may request withdrawal/destruction of their tissue samples up until the time that they are used for histology analysis by asking a study investigator. Should any research participants withdraw from study participation, they will be specifically asked if their collected samples may be studied per protocol.

This study will not obtain specimens from an existing bank/ repository, nor will there be any genetic research/testing.

5.5.8 Study Time Line

Please refer to Appendix J

5.6 Investigational Drugs/ Investigational Devices

5.6.1 Approval Status of Study Drugs

Not applicable.

5.6.2 Approval Status of Study Devices

The ReCell device used in this protocol is investigational meaning that it is not approved by the Food and Drug Administration (FDA) for use in the United States. This research project is being conducted under an Investigational Device Exemption (IDE) application and the ReCell device is categorized as a Category B, Class III under the FDA regulations. The operative procedure for this study is considered a research procedure.

The safety of ReCell has been demonstrated with over 5,000 treatment procedures conducted worldwide. ReCell has CE Marking in Europe, TGA clearance in Australia, SFDA clearance in China and Health Canada approval as well as approval in other markets (e.g., Taiwan, Hong Kong, Mexico, Brazil and Venezuela). There have been no reports of adverse events associated with the use of ReCell that have met the requirements for vigilance reporting to the respective regulatory authorities.

Investigational Product: Autologous Cell Harvesting Device (ReCell)

Dosing Instructions and Schedule: ReCell is supplied as a single use device. The contents of each kit are sufficient to prepare a cell suspension from a maximum biopsy size of 2cm x 2cm to cover a wound area up to and including 320cm² (*Note: each square cm of skin sample will treat 80 sq cm of treatment area*).

Proposed Indication: ReCell is intended to be used at point-of-care for the safe and rapid preparation of epidermal and dermal cells as well as the cells at the epidermal-dermal junction from a small sample of the patient's own skin. Under the provision of a healthcare professional, the cell suspension produced by the ReCell system is suitable for the treatment of partial-thickness wounds to promote re-epithelialization and for epidermal grafting over the INTEGRA™ MBWM.

Investigational Device Description: The investigational ReCell Autologous Cell Harvesting Device has been developed to provide a simple, safe technique for the harvesting of epidermal cells for epidermal repair. ReCell is a single-use, stand-alone, battery operated, autologous cell harvesting device kit that contains enzymatic and delivery solutions, sterile surgical instruments, and actuators. The contents of each kit are sufficient to prepare a cell suspension to cover a wound area up to and including 320cm².

This investigational device is used to disaggregate cells from a thin, shaved split-thickness skin biopsy sample obtained from the patient to be processed to produce a viable cell suspension for reintroduction to the patient.

After the skin sample is taken, the ReCell suspension is available in under 30 minutes for immediate use onto a prepared wound surface and can cover a wound 80 times the size of the skin sample (a thin, split-thickness shave biopsy of 0.15 mm - 0.2 mm depth delivers a 1:80 expansion ratio; meaning the cell suspension produced from each square cm of skin sample will treat 80 sq cm of treatment area). The delivered cell suspension enables quick epithelialization of the wound, usually in 5 to 7 days a site-matched skin sample allows reintroduction of the subject's own skin cells that will develop natural texture, vascularity (pinkness) and pigment.

The technology takes advantage of the regenerative capability of skin. Working with a small site-matched sample of the patient's healthy skin, ReCell produces a cell suspension that stimulates skin growth. The cell suspension, which is sprayed onto an affected area to be treated, contains the appropriate mixture of healthy cells to promote healing (*keratinocytes*), skin structure (*fibroblasts*), vascularity (*colour*), pigmentation (*melanocytes*) and texture.

The investigational product must be stored, handled and administered in accordance with this protocol, the manufacturer's IFU, as well as all applicable laws, regulations and institution requirements.

The Investigator will ensure control of the investigational device. The investigational devices will be administered only to those subjects enrolled in this study under the supervision of the investigator and under the terms of the clinical

protocol and Investigator's Agreement. All clinical supplies and study devices intended for use in the clinical study cannot be used, under any circumstances, for any purpose other than described in the protocol. The investigator will also ensure that the device components are maintained under secure storage and that device accountability records are maintained.

Investigational Device Accountability:

The Avita Medical Americas, LLC will supply the investigator with an adequate number of investigational devices for completion of the study. The investigator is responsible for ensuring all investigational product accountability. Any discrepancies must be described in writing. Throughout the study, device accountability records will be reviewed by the Sponsor's appointed clinical monitor. Records for dispensing study drug must be available for inspection by the clinical study monitor throughout the study. The investigator is responsible for ensuring that the device accountability records are complete and up to date at all times. Regular study device reconciliation will be performed to document device assigned to subject enrollment number by the clinical monitor.

The maintenance of study-related device accountability records does not preclude the Principal Investigator's responsibilities to maintain additional records in accordance with all national and/or local institutional requirements for investigational device use.

Receipt of Study Device:

Arrangements will be made to have the investigational device kits shipped from the manufacturer directly to the Investigational Pharmacy Services at WRNMMC, to the ATTN: [name], Departmental Chief, where they will be housed until ordered by the investigator for use.

The Principal Investigator, or a responsible party designated by the investigator, must maintain an inventory record to document the receipt and dispensation of each ReCell device kit.

The investigational pharmacist will be required to keep records pertaining to the total number of ReCell device kits received from the manufacturer, date of receipt, condition of kits upon receipt, location and conditions of storage for both ReCell device kit and enzyme, until use in the operating room will be recorded on forms provided in the Pharmacy Manual. Additionally, the investigational pharmacist will be required to record the lot number and expiration date for the Recell device kit and enzyme received. Any discrepancies must be described in writing.

Upon receipt of the of the study device supplies, an inventory must be performed and a device receipt log filled out and signed by the person accepting the shipment. It is important that the designated study staff counts and verifies that the shipment contains all the items noted in the shipment inventory. Any damaged or unusable study devices in a given shipment will be documented in the study files. The investigator must notify the study sponsor of any damaged or unusable study devices that were supplied to the investigator's site.

Investigational Device Packaging:

The ReCell device kit contains the following items provided in sterile packaging:

ReCell processing unit with built-in heating mechanism for warming the enzyme solution to optimum working temperature (+37°C)

Removable insert to act as a sterile Petri dish for use when preparing and scraping the skin biopsy

ReCell Enzyme

ReCell Buffer

Water

Syringes

Needles

Nozzles

Scalpel

Kits will be sealed with tamper resistant tape

ReCell Device Kit Labeling:

In accordance with The Code of Federal Regulations (CFR) 812.5 for investigational device labeling, the immediate package (outer box) of the ReCell kit bears the following information:

- The name, address, telephone number, facsimile number and website address of the manufacturer, Avita Medical Americas, LLC
- A separate label with the statement “**CAUTION – Investigational Device** Limited by Federal (or United States) Law to Investigational Use Only LBL090”
- Listing of package/kit contents
- Storage requirements to ensure stability of the investigational device and enzyme solution
- Label with various symbols identifying relevant contraindications, hazards, warnings, and precautions.
- Labels identifying investigational device kit date of manufacture, lot number and expiratory date of the product
- Label stating lot number and expiration date for enzyme solution

The ReCell kit and enzyme solution lot number and expiration date will be recorded in the eCRF.

Storage and Handling (refer to IFU, Appendix A):

The investigational device kits, including the enzyme (trypsin) will be maintained under controlled conditions.

Upon receiving ReCell, the pharmacist should examine the packaging for external signs of damage or tampering. If the external kit packaging or the packaging for any of the

individual components appears damaged, the kit should not be used. The pharmacist will be instructed to contact the investigator who in turn must notify the study sponsor of any damaged or unusable study devices that were supplied to the investigator's site.

To ensure stability of the device, storage requirements are as follows:

Once the contents of the kits have been inspected, the investigational pharmacist will remove the enzyme (trypsin) from each kit and immediately refrigerate at 2-8°C (35.6-46.4°F). The investigational pharmacist will be required to maintain a daily temperature log to record the temperature of the refrigerator where the enzyme is being stored. Any discrepancies must be described in writing.

All other components are to be stored at room temperature.

Dispensing of Investigational Device:

The investigational product (ReCell device) will not be applied to any person who is not a qualified study participant under this protocol. The ReCell device will be dispensed only by study site personnel designated by the Principal Investigator on the study site Delegation Log.

An order for the ReCell kit will be written by the Investigator and sent to the WRNMMC investigational pharmacy to request the treatment ReCell device kit for availability on the scheduled day of surgery for the subject enrolled.

When needed, the pharmacist will dispense 2 kits to a member of the research team. One ReCell kit will be dispensed for use and the other will be obtained for the purpose of having "on-hand" in the event of a device malfunction while in the operating room. The investigational pharmacist will record dispensing of both device kits. One kit will be denoted as "intended for use" and the second kit will be denoted as the "back-up device" in the device accountability log. If the second device deemed as the "back up device" was not needed, it will be returned to the investigational pharmacy by the study coordinator and logged back in on the device accountability log to be dispensed for future use with the next subject enrolled. Stringent record keeping of this dispensing process will be maintained for investigational device accountability.

The clinical site will utilize an investigational product accountability log provided by the manufacturer. The following information will be recorded on the log by the designated individual dispensing the investigational product: date investigational device(s) were dispensed and initials of device dispenser, subject number and lot number for device kits dispensed and documentation regarding date and lot number of returned "back-up device", if applicable.

Return or Destruction of Investigational Device:

At the completion of the study, there will be a final reconciliation of study devices shipped, devices consumed, and devices remaining. This reconciliation will be logged on the device reconciliation form, signed and dated by the Principal Investigator and the Investigational Pharmacist. Any discrepancies noted will be investigated, resolved, and documented prior to return or destruction of unused study devices.

ReCell and all individual components included in each kit are intended for single use only. Used ReCell devices and kit components will be discarded into appropriate biohazard receptacles after single use. Devices destroyed on site will be done in accordance with manufacturer recommendations, institutional policies and procedures and documented in the study regulatory files. Unused (including expired) investigational devices are to be returned to the manufacturer, Avita Medical Americas, LLC via use of their established Return Material Authorization (RMA) process. Per manufacturer directives, to return all unused investigational device kits, the study site will notify the manufacturer. They in turn will generate and send site an Investigational Device Return Form along with a return FedEx air bill to cover return shipment fees. The devices will be returned to the address below:

Return to:

Avita Medical
c/o Parker Hannifin Corp
ATTN: Customer Service
[name]
Ventura CA 93003
[contact]

5.7 Statistical Considerations

5.7.1 Study Endpoints

Primary Outcomes: Safety and Tolerability

The safety and tolerability endpoints for this feasibility clinical trial includes:

- Delayed healing/non-healing of wound and donor site
- Graft loss
- Heterotopic ossification
- Infection
- Scar contracture
- Durability (i.e. abrasions/injuries at graft site due to graft fragility)
- Allergic response to trypsin (the enzyme used in the ReCell process)
- Subject Complaint (i.e. pain and itching)
- Vital Signs
- Blood chemistries and hematology
- Treatment-related adverse events requiring surgical intervention prior to Week 12 post-treatment and all serious adverse event (SAE) occurrences throughout the study

Secondary Outcomes: Preliminary and Long-Term Efficacy

The preliminary efficacy (Week 1-6 post-treatment) endpoints for this feasibility clinical trial includes:

- Wound epithelialization 95% or greater re-epithelialization at treated wound site and donor sites
- Histology
- Patient pain rating

The long-term efficacy (Week 12 and 24 post-treatment) endpoints for this feasibility clinical trial includes:

- Scar assessment scale using the Patient and Observer Scar Assessment Scale (POSAS) and Vancouver Scar Scale
- Functional outcome rating
- Patient satisfaction
- Histology
- Radiographic evaluation for assessment of heterotopic ossification

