- Other Treatment-related adverse events requiring surgical intervention prior to Week 12 post-treatment and all serious adverse event (SAE) occurrences throughout the study.

We predict non-inferiority in safety measures between ReCell-treated areas and control

areas of the wound.

Specific Aim 2: Evaluate the **preliminary effectiveness** of ReCell treatment of full-thickness wounds treated with STSG over INTEGRA™ MBWM compared to a control site. Preliminary effectiveness will be assessed during an acute healing phase (Week 1–6) and will focus on healing of both wound and donor sites. Evaluations to be performed include:

- Wound epithelialization
- Histology
- Patient pain rating

We predict that, at each time point, more ReCell-treated areas will be healed to an extent defined as non-inferior compared to the control areas of the wound.

Specific Aim 3: Evaluate the **long-term effectiveness** of ReCell treatment of full-thickness wounds treated with INTEGRA™ MBWM compared to a control site. Long-term effectiveness will be assessed at Weeks 12 and 24 post-ReCell treatment. Evaluations will focus on the integrity and durability of regenerated tissue as well as physical characteristics such as pliability and cosmesis. Patient satisfaction will also be evaluated. Evaluations to be performed include:

- Scar assessment scale using the Patient and Observer Scar Assessment Scale (POSAS) and Vancouver Scar Scale
- Functional outcome rating
- Patient satisfaction
- Histology
- Radiographic evaluation for assessment of heterotopic ossification

We predict that scar/functional outcomes and patient satisfaction metrics will be non-inferior for ReCell treated areas.

INTRODUCTION TO STUDY CONDUCT

This document is a protocol for a human research study. This study is to be conducted according to US and international standards of Good Clinical Practice (International Conference on Harmonization ICH E6), the Code of Federal Regulations Title 21 parts 803 and 812, and other applicable government regulations and Institutional research policies and procedures. No amendment to the protocol or deviation from the protocol will be implemented without the prior review and approval of the Institutional Review Board (IRB) except where it may be necessary to eliminate an immediate hazard to a research participant. In such a case, the deviation will be reported to the IRB as soon as possible.

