Nozzle blockage	
 • Nozzles designed with an aperture which allows for cells to pass through easily • 100 micron filtration occurs prior to spraying of cells • Spare nozzle supplied with each device
Nozzle aperture position	
 • IFU recommend test spray • IFU describes aperture positioning

The potential risks to the subject and adverse events associated with use of the ReCell Device discussed in the tables above are minor and easily controlled.

Adverse Event Evaluations and Reporting

Subjects will be monitored for safety from time of enrollment to conclusion of study visits. All adverse events will be collected by direct subject communication with investigator/study coordinator and review of source documents.

At each post-treatment visit, the research team will assess if the subject has experienced any adverse effects post-treatment with the investigational device. The subject will be asked if he/she has any problems, issues and/or concerns since the last encounter visit that could be potentially related to study participation. Any conditions or symptoms reported after the subject receives investigational product will be recorded as an adverse event (AE) on the AE eCRF. This includes new events after study device administration, conditions

that become more severe or increase in frequency, any disease-related signs or symptoms present at the Screening Pre-Treatment visit that have worsen in severity or frequency, as well as any event or finding that the Investigator feels is clinically significant.

Other treatment-related adverse events requiring surgical intervention prior to Week 12 post-treatment and all serious adverse event (SAE) occurrences will be treated and recorded in the eCRF. For all adverse events, the Investigator will provide an assessment of the event, its treatment resolution, and relationship to the investigational device. Subjects who have an ongoing AE related to the study device at Week 24 post-treatment will be followed for 30 days until resolution and/or stabilization of the event at a level acceptable to the Investigator.

Adverse Event Definitions:

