Identification of Adverse Events (AEs), Adverse Device Effects (ADEs) An adverse event is defined as any new medical problem or exacerbation of an existing problem, experienced by a subject while enrolled in the study after receiving investigational product, whether or not it is considered related to the investigational device by the Investigator.

Treatment-Related Adverse Event

A treatment-related adverse event is an adverse event that is judged to be related to the investigational device, study therapy and study-related procedures.

Unexpected Adverse Event

An unexpected adverse event is any adverse effect which the frequency, specificity or severity is not consistent with the risk information described in the investigational plan.

Anticipated (Expected) Adverse Event

Potential adverse event that a subject may experience following the use of the ReCell device as described in this section above and using the potential risks listed in the above tables.

Definitions of Specific Major Treatment –Related Adverse Events:

Infection: The presence of infection for the ReCell treated areas and control site will be evaluated at each post-treatment visit. Infection will be evaluated in accordance with the Center for Disease Control (CDC) guidelines for nosocomial infections using standard clinical measures such as visual examination of the treatment sites for delayed healing, redness, inflammation and surrounding cellulitis. In the presence of symptoms (i.e., purulent exudate, changes in wound appearance such as hyperemia, and erythema in the uninjured skin surrounding the wound), infection will be confirmed using microbiological testing procedures and treatments initiated according to the institutions' infection management protocols, which will be recorded on the eCRF and Adverse Event form. Infection will be managed according to the standard protocols of the clinical site. For example, treatment of infection will involve the daily cleaning and dressing of wound sites until such time that the infection is clear. Treatment with broad spectrum antibiotics until microbiology sensitivities return from the testing laboratory is recommended. Upon return of sensitivities, antibiotic therapy may either continue as is, or be changed at the discretion of the investigator. All treatment regimens applied in the management of infection will be recorded on the eCRF.

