All observed or volunteered adverse effects (serious or non-serious) and abnormal test findings deemed clinically significant by the investigator, regardless of treatment group, if applicable, or suspected causal relationship to the investigational device or, if applicable, other study treatment or diagnostic product(s) will be recorded in the subjects’ eCRF. Criteria for grading of adverse events will be as defined by the Common Terminology Criteria for Adverse Events (CTCAE) version 4.0 (<http://www.upToDate.com/contents/common-terminology-criteria-for-adverse-events>). For all adverse effects, sufficient information will be pursued and/or obtained so as to permit 1) an adequate determination of the outcome of the effect (i.e., whether the effect should be classified as a *serious adverse effect*) and; 2) an assessment of the causal relationship between the adverse effect and the investigational device or, if applicable, the other study treatment or diagnostic product(s).

Severity

Each adverse event will be assessed for its severity, or the intensity of an event experienced by the subject, using the Common Terminology Criteria for Adverse Events (CTCAE), v4.0. The CTCAE grading (severity) scale will be utilized for each AE based on the following:

Grade 1 = Mild: Asymptomatic or mild symptoms; clinical or diagnostic observations only; intervention not indicated, discomfort noticed, but no disruption to daily activity

Grade 2 = Moderate: Minimal, local or noninvasive intervention indicated, discomfort sufficient to reduce or affect normal daily activity

Grade 3 = Severe: Medically significant but not immediately life-threatening; hospitalization or prolonged hospitalization indicated; disabling, inability to work or perform normal daily activity

Grade 4 = Life-threatening: Urgent intervention indicated

Grade 5= Death: Death related to an adverse event

Relationship of Adverse Events to the ReCell Investigational Device

The Investigator should assess the relationship of the adverse event to the investigational device. The relationship should be assessed using the following categories:

- **Definitely Related:**
A direct cause and effect relationship between the investigational device/treatment and the adverse event exists.
- **Likely Related:**
A direct cause and effect relationship between the investigational device/treatment and the adverse event has not been clearly demonstrated, but is likely or very likely.
- **Unlikely Related:**

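### The surgical-intervention part of the primary safety outcome admits only events judged treatment-related, under conflicting attribution rules, so its ReCell-versus-control count can be biased in either direction

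*Combined protocol and SAP*

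**What the plan says.** Section 5.7.1 makes safety and tolerability the primary outcome. One item reads "Treatment-related adverse events requiring surgical intervention prior to Week 12 post-treatment", and then adds all serious adverse events over the whole study. The relatedness condition applies to the first half of that item and not to the second. The same restriction appears in Section 3 (Specific Aim 1), in the Adverse Events paragraph of 5.5.4, in the safety analysis set of 5.7.3 and in 6.2.

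The item feeds a comparison. Specific Aim 1 states "We predict non-inferiority in safety measures between ReCell-treated areas and control" areas, and 5.7.3 summarises the listed safety items by treatment.

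On relatedness, 6.2 gives a broad definition: "A treatment-related adverse event is an adverse event that is judged to be related to the investigational device, study therapy and study-related procedures". Its operating instruction is narrower: "The Investigator should assess the relationship of the adverse event to the investigational device". The Adverse Events paragraphs of 5.5.4 and 6.2 likewise ask for relationship to the device, and 6.2 makes the principal investigator ultimately responsible for that attribution.

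On collection, 5.5.4 and the reporting part of 6.2 ask subjects about problems "since the last encounter visit that could be potentially related to study participation". An earlier paragraph of 6.2 has subjects asked about any adverse event since the previous visit.

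**The concern.** A count compared between two regions of one wound should admit events by the same rule in both. Here the entry rule is a causality judgement, most often worded as causality to a device that only one region receives. Re-operation on a region bears directly on whether a wider mesh is acceptable, and no other primary item records it region by region. If the entry rule works differently in the two regions, equal re-operation rates can look unequal, or a real difference can be hidden. Section 5.7.2 says the results may be used to refine a pivotal trial, so a distorted safety table would carry forward even though no formal test is planned here.

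**Working it through.** **1. The relatedness texts side by side**

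| Place | What relatedness refers to |
|---|---|
| 5.5.4, Adverse Events | Device |
| 6.2, Adverse Event Evaluations and Reporting | Device |
| 6.2, responsibility for attribution | Device |
| 6.2, instruction above the rating categories | Device |
| 6.2, definition of treatment-related | Device, study therapy and study procedures |
| 6.2, general recording paragraph | Device or, where applicable, other study treatment |
| 6.2, category wording | "A direct cause and effect relationship between the investigational device/treatment and the adverse event exists", that is, device or treatment |
| 5.7.3, tabulation of adverse events | Study treatment |

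No separate rating is provided for the control graft or for the procedure.

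**2. One event under both readings.** Take a control-region graft loss that needs regrafting before Week 12.
- Device reading: the region received no device, so the event is unrelated and is not counted.
- Definition reading: 5.6.2 calls the operation a research procedure, and 6.2 gives graft loss needing retreatment as its example of a major treatment-related event, without limiting it to one region. The event is related and is counted.

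Both codings follow the protocol.

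**3. Who codes.** Under 5.5.4 only the principal investigator and/or co-principal investigator apply the product. Under 6.2 the principal investigator is ultimately responsible for attribution. The blinding described in 5.1 and 5.5.4 covers the subject and the two scar observers, not attribution.

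**4. Size.** The plan has no figure to reproduce on this point. It gives no re-operation rate, and 6.2 says only that such events should be infrequent. The power table in 5.7.3 concerns a continuous outcome and has no bearing. The following is therefore an illustration under assumptions. Let n = 20, let p be the true rate in each region (no true difference), and let r and q be the probabilities that a ReCell-region and a control-region event are rated related.

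Expected counts: n·p·r versus n·p·q. Apparent difference: p·(r − q).

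With r = 1:

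| p | q = 1 | q = 0.5 | q = 0 |
|---|---|---|---|
| 5% | 1 v 1, gap 0 | 1 v 0.5, gap 2.5 points | 1 v 0, gap 5 points |
| 10% | 2 v 2, gap 0 | 2 v 1, gap 5 points | 2 v 0, gap 10 points |
| 20% | 4 v 4, gap 0 | 4 v 2, gap 10 points | 4 v 0, gap 20 points |

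The sign can reverse. If ReCell-region losses are put down to infection or the injury (r = 0) and control losses to the procedure (q = 1), then at p = 10% the count is 0 v 2, a gap of 10 points in ReCell's favour. If r = q = 0, the gap is 0, which matches the truth, but every event has left the table.

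**The case against.** Three objections have force.

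*The control region is not excluded by rule.* The definition, the category wording and the recording paragraph in 6.2 all reach beyond the device. A reader might infer that device causality is the only judgement collected and that every control regraft drops out. The text does not support that. What stands is that the texts disagree, and nothing says which one governs entry to the endpoint.

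*Other data catch these events.* Graft loss, delayed healing, infection, contracture and durability are separate primary items with no attribution condition. Under 5.5.4 the first four are expressly assessed in both regions at each post-treatment visit. All serious adverse events count. A reader might infer that the regions cannot be compared fairly on safety at all; that is too broad. However, these items do not show whether a region needed surgery. A regraft is a serious adverse event only if it meets the criteria in 6.2, such as prolonging hospitalization. Section 5.5.4 expects many subjects to be in-patients already, so some regrafts may not meet them. The adverse event listing in 5.7.3 does not name the region. Whether the sample eCRF (Appendix L) records it cannot be seen.

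*Subjects are not asked solely about study-related problems.* The narrow question in 5.5.4 and 6.2 could be read that way. But 6.2 also has the open question, source-document review and recording regardless of suspected cause, and 5.5.5 adds medical record review. What remains is an inconsistency in wording, and subjects blinded to region are poorly placed to judge relatedness.

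The Week 12 limit is not an error either. Specific Aim 1 justifies it by the period of greatest vulnerability to graft failure and continues safety monitoring to Week 24.

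**Conclusion.** The concern holds for the surgical-intervention component and no further. Its between-region count depends on a causality judgement with conflicting instructions, ultimately the responsibility of someone who may know the allocation. The documents do not fix the direction of the bias. With 20 subjects and equal true rates of 5%, 10% or 20%, the false gap reaches 5, 10 or 20 percentage points if all ReCell events and no control events are rated related. It falls to 0 if the two are rated related equally often. The rates and rating probabilities are assumptions. For scale only, 6.2 puts total graft loss at 5% to under 10% and partial loss at 10% or more, but neither is a re-operation rate or given by region. At one to four expected events per region, recoding one or two changes the reading. The study is descriptive (5.7.2, 5.7.3), so what is affected is the interpretation of the safety table, not a powered test. The change should be made.

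**What to change.** - In 5.7.1, and correspondingly in Specific Aim 1, 5.5.4, 5.7.3 and 6.2, replace the component with every unplanned surgical procedure on the A region, the B region or a donor site before Week 12, regardless of attribution. Record site and indication.
- Report it as a paired within-subject table for the two regions, with donor sites shown separately. Procedures through Week 24 may be added as a supplementary row; this is optional.
- Keep relatedness as a descriptor, not as a condition of entry. Reconcile its wording in 5.5.4 and 6.2 with the definition "judged to be related to the investigational device, study therapy and study-related procedures".
- Align the subject question in 5.5.4 and the reporting part of 6.2 with the open question earlier in 6.2.

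The cost is protocol wording, one table and, if the eCRF does not already hold them, fields for site and indication. Section 6.2 already requires events to be recorded whatever their suspected cause. The downside is small: some procedures done for the original trauma will be listed, and the indication field identifies them.
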